1 AMENDMENTS FROM PREVIOUS VERSION(S)

Included the initiation of 2nd line of therapy as a censoring event in the definition of progression-free survival. This was inadvertently omitted from the SAP and was identified after an author review of the definition provided in the manuscript draft.

2 INTRODUCTION

Note: in this document, any text taken directly from the non-interventional (NI) study protocol is *italicised*.

This study is designed to examine real-world use of palbociclib and aromatase inhibitor combination therapy in both male and female patients with A/MBC as first-line treatment.

All patients initiating palbociclib + an AI from the Syapse Learning Health Network dataset who meet the inclusion and exclusion criteria and initiated palbociclib combination therapy between February 2015 and July 2019 will be evaluated. This study is designed to describe patient characteristics, treatment patterns, and clinical effectiveness outcomes in a cohort of patients diagnosed with HR+/HER2- A/MBC who were treated with palbociclib combination with AI in the US community oncology setting.

2.1 Study Design

[figure not shown]
This is an observational, retrospective cohort study. Eligible patients will be identified from the Syapse Learning Health Network database and medical chart review will be conducted by Syapse Certified Tumor Registrars (CTRs). All study data are secondary data and will have been collected retrospectively from existing clinical data originally collected as part of routine care. This single-arm descriptive analysis will describe the patient characteristics, clinical attributes and treatment patterns of A/MBC patients with HR+/HER2- disease, who were treated with palbociclib + AI as first-line therapy. Additionally, clinical effectiveness outcomes for these patients will be evaluated between Feb 2015 and July 2019.

Study population

The study will include adult patients 18 years or older, diagnosed with HR+/HER2- A/MBC who initiated palbociclib combination therapy with AI as the first-line therapy on or after 03 February 2015 up to and including 31 July 2019. Patients for this study will be identified from the Syapse Learning Health Network database.

Preliminary analysis identified up to 1,074 patients with evidence of key primary inclusion criteria: breast cancer diagnosis and palbociclib treatment. Three to four hundred patients are expected to fulfil complete study inclusion criteria. Given the inclusion criterion requiring a qualifying treatment identification period between 03 February 2015 through 31 July 2019, and assuming a data cutoff date of 01 February 2020, the minimum follow-up available is therefore 6 months.

PFIZER CONFIDENTIAL

Data source

Patients will be identified and data will come from the Syapse Learning Health Network database which includes both inpatient and outpatient clinical and molecular data captured through manual abstraction and interoperative data feeds from a number of health system source systems, including:

- *Electronic medical record (EMR), including inpatient, outpatient oncology, ambulatory, surgical, etc.*
- *Electronic data warehouse (EDW)*
- *Laboratory information system (LIS)*
- *Picture archiving and communication system (PACS)*
- *Hospital based cancer registries*
- *Computerized physician order entry (CPOE)*

- *Additionally, Syapse augments health system data with the Surveillance, Epidemiology, and End Results (SEER) national cancer registry, other regional registries, the Social Security Death Index (SSDI), digitized obituary data. In order to capture complete and accurate vital status and dates of death, Syapse brings together data from multiple sources to create a composite view of patients' mortality (including EHR, hospital registry, manual abstraction, digital obituaries (such as tributes.com and legacy.com), Social Security Death Index, and SEER). Syapse is in the process of validating the completeness and accuracy of the Syapse mortality composite score versus the National Death Index (NDI), a centralized database of death records. Initial analysis shows that the combined Syapse Data Sources are very accurate. More detailed information forthcoming in the data management document.*

Treatment/cohort labels

Data from patients with only one treatment group labelled as palbociclib + AI are explored in this retrospective study.

2.2 Study Objectives

Primary Objectives:

- 1) *Among patients with HR+/HER2- A/MBC receiving palbociclib combination therapy with AI as first-line therapy:*
 - a. *Describe demographic and clinical characteristics.*
 - *Demographic characteristics will include age, sex, race, insurance status, menopausal status, and region of residence at A/MBC diagnosis.*

[figure not shown]
PFIZER CONFIDENTIAL

- *Clinical characteristics will include variables such as, stage of initial diagnosis, histology, Eastern Cooperative Oncology Group (ECOG) performance status (where ECOG score unavailable, Karnofsky performance status will be converted to corresponding ECOG score) and comorbid disease burden utilizing the Charlson Comorbidity Index, HER2 and estrogen receptor (ER)/ progesterone receptor (PR) status, BRCA status, number and sites of distant metastasis at A/MBC diagnosis (visceral (defined as liver, lung, peritoneum, and pleural nodules), non-visceral, bone only); modalities of treatment received prior to A/MBC diagnosis (chemotherapy, hormone therapy, surgery, radiation therapy) documentation of endocrine sensitivity and endocrine resistance if hormone therapy was received in the adjuvant setting, time to metastasis (time between initial and metastatic diagnosis) and disease free interval (time between completion of adjuvant therapy and diagnosis of A/MBC).*
- b. *Describe treatment patterns.*
 - *Distribution of regimens from the diagnosis of A/MBC through the end of the record.*
 - *Sequence of regimens across lines, through the end of the record of systemic therapy.*
 - *Description of the dosing will include the starting dose, end dose, dose adjustment (dose increase and dose reduction), type of dose adjustment (dose modification, schedule changes, dose delay, or hold) discontinuation, reason (including progression, end of planned therapy, insurance changes, schedule change, dose delay, hold, cost, patient refusal, toxicity), and time to dose adjustment (discontinuation).*
- 2) *Among patients receiving palbociclib + AI as first-line therapy, examine clinical effectiveness outcomes including:*
 - a. *Real-world progression-free survival (rwPFS) will be assessed for the first-line therapy.*
 - b. *Real-world overall survival (rwOS) will be assessed from the start of the first-line therapy.*
 - c. *Real-world time to next therapy (rwTTNT) will be assessed from the start of the first-line therapy.*
 - d. *Real-world time to treatment discontinuation (rwTTD) will be assessed from the start of the first-line therapy.*
 - e. *Real-world time to chemotherapy (rwTTC) will be assessed from the start of the first-line therapy.*
 - f. *Real-world time to dose adjustment (rwTTDA) will be assessed from the start of the first-line therapy.*

3 HYPOTHESES AND DECISION RULES

Not Applicable

PFIZER CONFIDENTIAL

4 ANALYSIS SETS/POPULATIONS

Analysis population will be all patients identified from the Syapse Learning Health Network database who meet the following inclusion and exclusion criteria-

Inclusion criteria

Patients must meet all of the following inclusion criteria to be eligible for inclusion in the study:

1. *Female or male sex.*
2. *Diagnosis (confirmed by clinical review) of A/MBC, defined as breast cancer at stage IIIB, stage IIIC, stage IV or identified as having distant metastasis.*
3. *Age ≥ 18 years at A/MBC diagnosis.*
4. *Initiated palbociclib in combination with an AI as first-line therapy after A/MBC diagnosis on or after 03 February 2015 through 31 July 2019. Note that the date of the start of the inclusion period reflects the month of palbociclib US FDA approval.*
5. *Evidence of ER or PR positive disease, or absence of any indication of ER and PR negative disease closest to A/MBC diagnosis (ie patients are eligible without affirmative indication of ER/PR+ status as long as ER/PR- indication is not present).*
6. *Evidence of HER2 negative disease, or absence of any indication of HER2 positive disease closest to A/MBC diagnosis (ie patients are eligible without affirmative indication of HER2- status as long as HER2+ indication is not present).*

Exclusion criteria

Patients meeting any of the following criteria will not be included in the study:

[figure not shown]
[figure not shown]
1. *Enrollment in an interventional clinical trial for A/MBC during the study observation period.*
2. *Evidence of prior treatment with any CDK4/6 inhibitor in the adjuvant setting (i.e. a CDK4/6 inhibitor is administered (start date) > 30 days prior to the A/MBC diagnosis date).*
3. *Evidence of another primary cancer within 3 years prior to the initial line containing palbociclib.*

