Kaplan-Meier survival analysis is used to descriptively characterize time to event outcomes. In this study, following time to event outcomes will be analyzed-

- Time to Real-world overall survival (rwOS)

[figure not shown]
The time origin for analysis of rwOS is start of the first-line therapy, and the terminal event is death. For patients not known to be deceased at the time of analysis, rwOS will be censored at the earliest of the last date of last contact or the end of the study period.

- Time to Real-world progression-free survival (rwPFS)

The time origin for analysis of rwPFS is start of the first-line therapy. Patients without a clinician-assessed progression event or death will be censored at the earliest of the following events: date of initiation of the 2nd line for patients with >1 line of therapy, date of last contact, or end of study period.

- Real world time to treatment discontinuation (rwTTD)

PFIZER CONFIDENTIAL

The time origin for analysis of rwTTD is start of the first-line therapy. Patients without first-line treatment discontinuation and who did not die will be censored at the earliest of the following events: last known usage of first-line treatment, or end of study period.

- Real world time to next treatment (rwTTNT)

The time origin for analysis of rwTTNT is start of the first-line therapy. Patients without a subsequent line of therapy initiation and who did not die will be censored at the earliest of the following events: date of last contact, or end of the study period.

- Real world time to chemotherapy (rwTTC)

The time origin for analysis of rwTTC is start of the first-line therapy. Patients who did not receive subsequent chemotherapy and who did not die will be censored at the latest of the following events: date of last contact, or end of the study period.

- Real world time to dose adjustment (rwTTDA)

The time origin for analysis of rwTTDA is start of the first-line therapy. Patients without a first-line treatment dose adjustment will be censored at the earliest of the following events: first-line treatment discontinuation, date of death, date of last contact, or end of the study period.

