8.2.3 Medication/ Treatment Data

Treatment Patterns

PFIZER CONFIDENTIAL

[figure not shown]

Table 15.4.1. Total Number of Lines Per Patient from the Diagnosis of A/MBC

Variable, n (%)	palbociclib + AI (n=xxx)
1	n (x.x%)
2	n (x.x%)
3	n (x.x%)
4	n (x.x%)
≥5	n (x.x%)

Table 205.4.2. Treatments by Line of Therapy from the Diagnosis of A/MBC

Line	Regimen (Agents)	palbociclib + AI (n=xxxx)
1 (N=xxx)	XXXXXX	n (x.x%)
	XXXXXX	n (x.x%)
	XXXXXX	n (x.x%)
	...	
2 (N=xxx)	XXXXXX	n (x.x%)
	XXXXXX	n (x.x%)
	XXXXXX	n (x.x%)
	...	
3 (N=xxx)	XXXXXX	n (x.x%)
	XXXXXX	n (x.x%)
	XXXXXX	n (x.x%)
	...	
	XXXXXX	n (x.x%)
4 (N=xxx)	XXXXXX	n (x.x%)
	XXXXXX	n (x.x%)
	XXXXXX	n (x.x%)
	...	
5 (N=xxx)	XXXXXX	n (x.x%)
	XXXXXX	n (x.x%)
	XXXXXX	n (x.x%)
	...	

Figure 215.4.3. Proportion of Patients with Regimen by Line of Therapy from the Diagnosis of A/MBC

PFIZER CONFIDENTIAL

Dosing Description

Table 15.4.4. Dosing at Start and End of Treatment, n (%)

Starting dose	End dose				
	75mg	100mg	125mg	Unknown	Total
75 mg	n (x.x%)				
100 mg	n (x.x%)				
125 mg	n (x.x%)				
Unknown	n (x.x%)				
Total	n (x.x%)				

Table 15.4.5. Dosing description

Variable/Statistic	palbociclib + AI (n=xxx)
Dose adjustment	
No adjustment	n (x.x%)
Increase	n (x.x%)
Decrease	n (x.x%)
Unknown	n (x.x%)
Type of dose adjustment	
Hold	n (x.x%)
Schedule change	n (x.x%)
Dose delay	n (x.x%)
Hold	n (x.x%)
Cost	n (x.x%)
Patient refusal	n (x.x%)
Toxicity	n (x.x%)
Time (days) to Dose Adjustment	
n	xx
Mean (SD)	x.x (x.xx)
Median (Q1, Q3)	x.x (x.x, x.x)
Min, Max	x.x, x.x
Discontinuation	
No	n (x.x%)
Yes	n (x.x%)
Discontinuation reason	
Progression	n (x.x%)
Intolerance/Toxicity	n (x.x%)
Other/Unknown	n (x.x%)
Patient choice	n (x.x%)
Treatment for other diseases	n (x.x%)
Left health system	n (x.x%)
End of planned therapy	n (x.x%)
Changes in insurance	n (x.x%)
Death	n (x.x%)
Hospice referral	n (x.x%)

PFIZER CONFIDENTIAL

[figure not shown]
Table 15.4.5. Dosing description

Variable/Statistic	palbociclib + AI (n=xxx)
Physician choice	n (x.x%)
Treatment ongoing	n (x.x%)

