ER, PR, HER2 test type	ISH, IHC, NGS, PCR, Other, Unknown
ER, PR, HER2 sample collection date	Year, month, day
ER, PR, HER2 report date	Year, month, day
BRCA status	BRCA1 Mutation; BRCA2 Mutation; BRCA NOS Mutation
BRCA sample collection date	Year, month, day
BRCA report date	Year, month, day
Treatment modalities prior to A/MBC diagnosis	
Breast surgery	Yes; No
Surgery type	Partial mastectomy; Lumpectomy / excisional biopsy; Segmental mastectomy; Subcutaneous mastectomy; Total mastectomy; Modified radical mastectomy; Radical mastectomy; Extended radical mastectomy; Mastectomy, NOS; Surgery, NOS
Note: if multiple, all will be listed (longitudinal data)	

PFIZER CONFIDENTIAL

Surgery date	Year, month, day
Breast radiation therapy	Yes; No
Radiation therapy site	Whole breast; Partial breast; Chest wall; Regional lymph nodes; Unknown Note: limited to primary breast cancer site. If multiple, all will be listed (longitudinal data)
Radiation start/end dates	Year, month, day
Chemotherapy	Yes; No
Recurrence	
Patient had recurrence	Yes; No
Recurrence date	Year, month, day (Captures first time locally, first time regionally, and first time distant; if multiple sites, hierarchy prioritizes most advanced site)
Recurrence site	Local; Regional; Distant; Unknown
Recurrence test source	Biopsy; Imaging; Imaging confirmed by biopsy; Unknown
Clinician confirmation of recurrence	Sources including: Medical oncology consult/note; Radiation oncology note; Discharge summary; Other
Recurrence linked to therapy	Yes; No
Progression	
Patient had progression	Yes; No
Progression date	Year, month, day
Progression test source	Biopsy; Imaging; Imaging confirmed by biopsy; Unknown
Clinician confirmation of progression	Sources including: Medical oncology consult/note; Radiation oncology note; Discharge summary; Other
Clinician confirmation date	Year, month, day

[figure not shown]
PFIZER CONFIDENTIAL

Progression linked to therapy	Yes; No
Complete systemic therapy history	
Therapy name	Therapy name
Administration route	Categories including: Oral; Infusion; Injection; Other; Unknown

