Real-world progression free survival (rwPFS)	Length of time from the start of palbociclib + AI treatment to the earliest of the following: clinician-assessed progression event, date of death, date of last contact, or end of study period. Progression identified from tissue/pathology or imaging/radiology and confirmed by clinician (in 2 separate data points), from MA guidance: 
1. Medical Oncology Consult/Note (can also include medical oncologist history and physical (H&P))2. Radiation Oncology note/consult/(can also include radiation oncology H&P)3. Progress Note (can also include /H&P/Consult - use this option for physician of other discipline in the absence of numbers 1 and 2)4. Discharge Summary5. Nursing Note6. Care Everywhere/Scanned Documents/External lab reports (for information diagnosed outside of facility for which patient is being abstracted)7. Other
Real world time to treatment discontinuation (rwTTD)	Length of time from the start of palbociclib + AI treatment to the earliest of the following: date the patient discontinues first-line treatment, date of death, last known usage of first-line treatment, or end of study period
Real world time to next treatment (rwTTNT)	Length of time from the start of palbociclib + AI treatment to the earliest of the following: subsequent line of therapy initiation, date of death, date of last contact, or end of the study period

Real world time to dose adjustment (rwTTDA)	Length of time from the start of palbociclib + AI treatment to the earliest of the following: date of first-line treatment dose adjustment, date of death, last known usage of first-line treatment, or end of study period.
Real world time to chemotherapy (rwTTC)	Length of time from the start of palbociclib + AI treatment to the earliest of the following: the day before the start of subsequent chemotherapy for patients with evidence of chemotherapy, or date of death for any reason. Or, where censored, the latest of date of last contact, or end of the study period.

PFIZER CONFIDENTIAL

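### No network contact is required at or before palbociclib + AI start and late entry is not handled, so rwOS and the other time-to-event estimates may be biased if some patients joined the network after starting

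*SAP*

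**What the plan says.** **Population.** Section 4: "Analysis population will be all patients identified from the Syapse Learning Health Network database who meet the following inclusion and exclusion criteria". Six inclusion and three exclusion criteria follow. Inclusion criterion 4 dates the treatment: "Initiated palbociclib in combination with an AI as first-line therapy after A/MBC diagnosis on or after 03 February 2015 through 31 July 2019". None of the nine criteria concerns where treatment began, whether the patient had been seen in the network by then, or any activity window around the start.

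**Data captured.** Appendix 2 (Section 9.2) includes "Complete systemic therapy history", with start and end dates and no limit to therapy given inside the network. For confirming progression it also accepts "Care Everywhere/Scanned Documents/External lab reports (for information diagnosed outside of facility for which patient is being abstracted". Tables 15.1.17 and 15.1.18 list the same kinds of outside source for progression and recurrence before first-line therapy. Appendix 2 has a last contact date but no first contact date. Table 15.4.5 lists "Left health system" as a reason for discontinuation.

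**Analysis.** Section 7.2: "The time origin for analysis of rwOS is start of the first-line therapy, and the terminal event is death". For patients not known to have died, "rwOS will be censored at the earliest of the last date of last contact or the end of the study period". On the method: "Kaplan-Meier survival analysis is used to descriptively characterize time to event outcomes"; one Cox model per endpoint is added. No entry date, left truncation or related sensitivity analysis is mentioned.

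**The concern.** Suppose a patient starts palbociclib + AI at an outside practice and first attends a network system a year later. If the outside start is abstracted, the patient meets every criterion and is followed from that start. A similar patient who died before any transfer never enters the database. The first patient's year is therefore immortal time, yet ordinary Kaplan-Meier and Cox count it as time at risk. The composite mortality source in Section 2.1 does not help, because it completes deaths only for patients already identified.

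rwOS is one of the study's primary effectiveness outcomes, and the single-arm design has no comparator in which a similar bias might cancel. With no first contact date among the listed variables, the analyst could not tell whether the problem exists.

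**Working it through.** **1. The plan's own figure.** Section 2.1 gives a minimum follow-up of 6 months. From 31 July 2019 to the assumed cutoff of 01 February 2020 is 185 days; 185 / 30.4375 = 6.08 months, so it reproduces. From 03 February 2015 the maximum is 59.9 months. Censoring was therefore simulated as uniform on 6 to 60 months.

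**2. Mechanism.** Let λ be the true death rate. A patient who has not yet entered cannot be observed to die, so with entry unrelated to prognosis the ordinary Kaplan-Meier hazard at time t is

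λ × (share of those counted at risk at t who have already entered).

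For a median of 36 months, λ = ln 2 / 36 = 0.0193 per month. If 30% of the cohort enter late, the estimated hazard just after time zero is 0.0193 × 0.70 = 0.0135. It approaches λ as the late entrants arrive.

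**3. Size when entry is unrelated to prognosis.** The SAP gives no rwOS, transfer-in share or delay, so these are assumptions: exponential survival with median 36 or 48 months, 5-30% late entrants, and exponential delay with mean 6, 12 or 18 months. Late entrants were kept only if alive and uncensored at entry, with 400,000 patients per setting. True 24-month survival is 0.5^(24/36) = 63.0% and 0.5^(24/48) = 70.7%.

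| Late share / mean delay | Ordinary KM, true median 36: median; 24-month | Ordinary KM, true median 48: median; 24-month |
|---|---|---|
| 5% / 6 mo | 36.2; 63.3% | 48.5; 71.2% |
| 10% / 12 mo | 36.9; 64.1% | 49.0; 71.7% |
| 20% / 12 mo | 38.0; 65.3% | 49.9; 72.6% |
| 30% / 18 mo | 39.8; 67.2% | 52.0; 74.2% |

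Over all settings the ordinary median was 36.2-39.8 against 36, and 48.4-52.0 against 48. The shift is about 0.2 to 4 months. At 24 months it is about 0.3 points (63.3 − 63.0) to 4 points (67.2 − 63.0 = 4.2). Delayed-entry Kaplan-Meier recovered the true values to within simulation error.

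**4. Size when transfer follows progression.** Assumptions: median time to progression 20 months, median survival after progression 22 months, death without progression at 0.004 per month, and entry within 2 months after progression. The true median is about 45 months.

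| Late share | Ordinary KM median | Delayed-entry KM median |
|---|---|---|
| 10% | 44.2 | 43.0 |
| 20% | 43.5 | 41.0 |
| 30% | 42.9 | 39.1 |

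The ordinary median is now too low by about 1 to 2 months, and delayed entry moves it further from the truth. Twelve-month survival is still marginally high (90.4-90.6% against about 90.2%), so the direction can also differ along the curve.

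**The case against.** **No evidence of transfer-in.** Nothing in the SAP says that any patient started treatment elsewhere. The outside-records item belongs to the list of sources for confirming progression, and the health-system item in Table 15.4.5 records patients leaving, not arriving. Appendix 2 collects insurance and menopausal status at palbociclib initiation, and performance status within 60 days of it, which suggests that patients were expected to be under observation then. All this stands. What remains is that the therapy history is not limited to network care, that Tables 15.1.17 and 15.1.18 accept outside records for events before first-line therapy, and that nothing excludes late entrants.

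**The protocol may hold a network-activity rule.** It was not available here. But the criteria are marked as protocol text, and Section 4 takes all patients who meet them.

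**A reader might infer that rwOS is overstated and that delayed entry corrects it.** The SAP supports neither inference. Both need late entrants to exist and entry to be unrelated to prognosis; step 4 shows that both can fail.

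**The effect may be lost in sampling error.** With 300-400 patients and 24-month survival near 66%, the 95% half-width before censoring is 1.96 × √(0.66 × 0.34 / n), which is 5.4 points at n = 300 and 4.6 at n = 400. The shifts in step 3 are smaller, and Section 3 sets no hypothesis that could be affected. This limits the weight of the point. It does not remove it, because a confidence interval does not allow for bias.

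**Conclusion.** The gap is real: there is no network-contact condition at treatment start, an outside start could be captured, and all patients are counted at risk from that start. Whether it biases the results depends on whether patients entered late, which the SAP does not show.

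If they did, rwOS is biased upward when entry is unrelated to prognosis, by about 0.2-4 months in the median and 0.3-4 points at 24 months under the assumptions of step 3. The median may be biased downward when transfer follows progression. The other time-to-event endpoints share the time origin and may also be biased, in a direction that depends on why patients transfer. With no late entrants nothing changes. This is a cheap safeguard worth adding, not a demonstrated error in the estimates.

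**What to change.** 1. Add the date of first network contact to Appendix 2.
2. Report in Table 15.1.1 how many patients started palbociclib + AI before that date, and summarise the delay.
3. In Section 7.2, repeat the Kaplan-Meier and Cox analyses in patients with network contact on or before treatment start, or make this an inclusion condition in Section 4. This removes selection through transfer-in whatever prompted the transfer; the result then describes patients already in network care when they started.
4. If a delayed-entry analysis is added, with entry at the later of treatment start and first network contact, label it supportive and state that it is valid only if entry is unrelated to prognosis.

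Cost: one further date to extract and a slightly smaller restricted sample. The SAP does not list this date as already held. Since Appendix 2 makes exact last-contact dates depend on the de-identification approach, the same limit may apply here.
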